4.9.2 Statistical / Analytical Issues

4.9.2.1 Handling of Dropouts or Missing Data

Missing values will not be substituted by estimated values, but treated as missing in the statistical evaluation. All data from all subjects dosed in the study will be included in all listings, plots, summary tables, and statistical analyses when appropriate.

4.9.2.2 Interim Analyses and Data Monitoring

Safety information will be monitored on a continuing basis to support decisions regarding dose finding in Phase 1 and cohort expansion in Phase 2. Guided by Simon's 2-stage design, tumor response rates together with other relevant observations such as duration and depth of response will be evaluated after Stage 1 enrollment is complete; these results will be reviewed by the SRC as a basis for benefit risk assessment and decisions regarding Stage 2 enrollment. The assumed historic and target response rates at the time of protocol finalization may have been changed over time and may need to be adjusted by the time of the data evaluation.

4.10 Pharmacokinetic Analysis

Pharmacokinetic parameters of C_{\min} and C_{\max} for mogamulizumab and C_{\min} for nivolumab will be summarized at each infusion for the Pharmacokinetic Analysis Set. Descriptive summary statistics including mean, standard deviation, coefficient of variation (CV), median, range, geometric mean, and coefficient of variation based on geometric mean will be presented. Individual serum C_{\min} or C_{\max} for mogamulizumab will be shown to one decimal place. If a C_{\min} or C_{\max} for mogamulizumab is below the lower limit of quantification (BLQ, <12.5 ng/mL), the concentration will be shown as "BLQ" in a listing, and the data will be handled as 0 ng/mL when calculating descriptive statistics. If the mean, minimum, median, or maximum is calculated to be below the lower limit of quantification, it will be shown as "BLQ" in a table. If the mean is below the lower limit of quantification, standard deviation will be shown as dash ('-') in the table.

4.11 Pharmacodynamic Analysis

Pharmacodynamic data will be summarized in a separate stand alone report according to a dedicated biomarker analytical plan.

4.12 Immunogenicity Analysis

4.12.1 Sample Anti-Mogamulizumab Antibody (ADA) Status

For a given sample, the ADA status for anti-mogamulizumab antibody will be determined using the anti-mogamulizumab antibody assay results (both screening and confirmatory), along with the serum mogamulizumab concentration at the same time point as follows.

- ADA-positive: The sample is positive in the confirmatory assay.
- ADA-negative: The sample is negative in the screening assay and the serum mogamulizumab concentration at the same time point is equal to or less than the drug tolerance limit (16000 ng/mL), or the sample is positive in the screening assay and negative in the confirmatory assay.
- ADA-inconclusive: The sample is negative in the screening assay and the serum KW-0761 concentration at the same time point is above the drug tolerance limit (16000 ng/mL).
- ADA-unknown: The sample is negative in the screening assay and the serum KW-0761 concentration at the same timepoint is unknown.

4.12.2 Sample Anti-Mogamulizumab Neutralizing Antibody (NAb) Status

For a given sample, the anti-mogamulizumab neutralizing antibody (NAb) status will be determined using the NAb assay result as follows.

- NAb-positive: The sample is positive in the NAb assay.
- NAb-negative: The sample is negative in the NAb assay.

4.12.3 Subject ADA Status

Each subject will be assigned a “subject ADA status” at baseline and at each subsequent time point during mogamulizumab administration.

A subject whose baseline (before administration of mogamulizumab) sample ADA status is ADA-positive will be classified as “Baseline-positive”.

During mogamulizumab administration, a subject ADA status will be determined as follows:

- ADA-positive: The subject’s samples meet either of the following criteria.
 - Treatment-induced ADA: The assay result of the sample before administration of KW-0761 is negative and one or more assay results of the samples after administration of mogamulizumab are positive.
 - Treatment-boosted ADA: The assay result of the sample before administration of mogamulizumab is positive and one or more titer values of the samples

after administration of mogamulizumab are ≥ 16 -fold of the titer value in the sample before administration of mogamulizumab.

- ADA-negative: Subject ADA status is not defined as “ADA-positive” at any time point and the sample ADA status at the last time point is not “ADA-inconclusive”.
- ADA-inconclusive: Subject ADA status is not defined as “ADA-positive” at any time point and the sample ADA status at the last time point is “ADA-inconclusive”.

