4.12.5 Determination of Anti-Mogamulizumab Antibody Incidence

The ADA analysis set for mogamulizumab will include all subjects that have both a baseline subject ADA status and at least one on-treatment subject ADA status.

The following percentage will be determined using baseline samples:

- Pre-existing ADA incidence: The number of the subjects whose ADA status is “Baseline-positive” (as defined in 4.12.3) as a percentage of the total number of subjects in the ADA Analysis Set.

The following percentages will be determined using on-treatment samples:

- Overall ADA incidence: The number of subjects whose subject ADA status is “ADA-positive” (as defined in 4.12.3) as a percentage of the total number of subjects in the ADA Analysis Set.
- Treatment-induced ADA incidence: The number of subjects who have “Treatment-induced ADA” (as defined in 4.12.3) as a percentage of the number of subjects whose sample ADA status before administration of mogamulizumab is “ADA-negative” (as defined in 4.12.3).
- Treatment-boosted ADA incidence: The number of the subjects who have “Treatment-boosted ADA” (as defined in 4.12.3) as a percentage of the number of subjects whose subject ADA status is “Baseline-positive” (as defined in 4.12.3).
- Neutralizing ADA incidence: The number of subjects whose subject ADA status is “NAb-positive” (as defined in 4.12.3) as a percentage the number of subjects in the ADA Analysis Set.

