Study terminated	xx (xx.x)
Other	xx (xx.x)
Subjects Who are Ongoing with the Study	xx (xx.x)

Note: Percentage is calculated using the number of enrolled subjects as the denominator.

Programming note: First page of this table is for "All Cancer Types; subsequent pages are for NSCLC SQ, NSCLC NSQ, NSCLC NSQ PD-L1 non-expressing, Ovarian, CRC, SCCHN, HCC, Pancreatic cancer types separately. "Ongoing" rows will be removed after DBL.

Table 14.1.1.3
Data Sets Analyzed
All Subjects Enrolled

All Cancer Types

	Mogamulizumab x mg/kg + Nivolumab 240 mg n (%)
Subjects Enrolled	xx (100.0)
Safety Analysis Set	xx (xx.x)
Reason for Exclusion from Analysis Set	
Did not receive any study drug	xx (xx.x)
Efficacy Analysis Set	xx (xx.x)
Reason for Exclusion from Analysis Set	
Did not receive combination medication at cycle 1 day 1	xx (xx.x)
Did not receive Mogamulizumab at cycle 1 day 1	xx (xx.x)
Did not receive Nivolumab at cycle 1 day 1	xx (xx.x)
Pharmacokinetic Analysis Set	xx (xx.x)
Reason for Exclusion from Analysis Set	
Did not have any post baseline concentration	xx (xx.x)
ADA Analysis Set for Mogamulizumab antibody	xx (xx.x)
Reason for Exclusion from Analysis Set	
Did not have baseline sample	xx (xx.x)
Did not have any post baseline sample	xx (xx.x)

Note: Percentage is calculated using the number of enrolled subjects as the denominator.

Programming note: First page of this table is for "All Cancer Types; subsequent pages are for Phase 1 Cohort, NSCLC SQ, NSCLC NSQ PD-L1 non-expressing, Ovarian, CRC, SCCHN, HCC, Pancreatic cancer types separately.

Table 14.1.2.1.1
Demographic and Baseline Disease Characteristics
Safety Analysis Set

Variable Statistic/Category	Mogamulizumab x mg/kg + Nivolumab 240 mg N=xxx
Age (years) at time of informed consent	
n	xx
Mean	xx.x
Std Dev	xx.xx
Median	xx.x
Minimum	xx
Maximum	xx
Age Group (n, %)	
<65 years	xx (xx.x)
>=65 years	xx (xx.x)
Gender (n, %)	
Male	xx (xx.x)
Female	xx (xx.x)
Child-bearing potential	xx (xx.x)
Race (n, %)	
White	xx (xx.x)
Asian	xx (xx.x)
Black or African American	xx (xx.x)
American Indian or Alaska Native	xx (xx.x)
Native Hawaiian or Other Pacific Islander	xx (xx.x)
Not reported	xx (xx.x)
Other	xx (xx.x)
Ethnicity (n, %)	
Hispanic or latino	xx (xx.x)
Not hispanic or latino	xx (xx.x)
Not reported	xx (xx.x)
Unknown	xx (xx.x)

Note: Percentage is calculated using the number of subjects in the column heading as the denominator.

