Programming note: First page of the table is for "All Cancer Types". Subsequent pages are for NSCLC SQ, NSCLC NSQ PD-L1 non-expressing, Ovarian, CRC, SCCHN, HCC, Pancreatic cancer types separately.

Table 14.5.1.1
Number (%) of Subjects with Positive Anti-Drug Antibody Response to Mogamulizumab
ADA Analysis Set

All Cancer Types

Visit	Mogamulizumab x mg/kg (N=xxx)	
	Anti-Mogamulizumab Antibody	Anti-Mogamulizumab Neutralizing Antibody
	n/N1 (%)	n/N2 (%)
Cycle 1/Day 1 (Baseline)	x/xx (xx.x)	x/xx (xx.x)
Overall	x/xx (xx.x)	x/xx (xx.x)
Cycle 2/Day 1	x/xx (xx.x)	x/xx (xx.x)
Cycle 3/Day 1	x/xx (xx.x)	x/xx (xx.x)
Cycle 4/Day 1	x/xx (xx.x)	x/xx (xx.x)
Cycle 8/Day 1	x/xx (xx.x)	x/xx (xx.x)
Cycle 12/Day 1	x/xx (xx.x)	x/xx (xx.x)
100-110 Days after Last Dose	x/xx (xx.x)	x/xx (xx.x)
During an Infusion-related Reaction	x/xx (xx.x)	x/xx (xx.x)

N1: Number of subjects with valid measurements for anti-mogamulizumab antibody at the specified visit

N2: Number of subjects who were positive for anti-mogamulizumab antibody at the specified visit

Overall is positive if at least one post-baseline assessment is positive, including unscheduled ADA assessments.

Programming note: This table is for all cancer types. Display: "All Cancer Types". Subsequent pages are for NSCLC SQ, NSCLC NSQ PD-L1 non-expressing, Ovarian, CRC, SCCHN, HCC, Pancreatic cancer types separately.

Table 14.5.2.1
 Summary of Anti-Mogamulizumab Antibody Incidence
 ADA Analysis Set

All Cancer Types

ADA Incidence				
Pre-existing	Anytime	Treatment-induced	Treatment-boosted	Neutralizing ADA Incidence
n/N (%)	n/N (%)	n/N1 (%)	n/N2 (%)	n/N (%)
x/xx (xx.x)	x/xx (xx.x)	x/xx (xx.x)	x/xx (xx.x)	x/xx (xx.x)

n: The number of subjects who were categorized at each item.

N1 : Number of subjects whose sample ADA status at pre-infusion in Cycle 1 Day 1 was "ADA-negative".

N2 : Number of subjects whose sample ADA status at pre-infusion in Cycle 1 Day 1 was "ADA-positive".

Programming note: This table is for all cancer types. Display: "All Cancer Types". Subsequent pages are for NSCLC SQ, NSCLC NSQ PD-L1 non-expressing, Ovarian, CRC, SCCHN, HCC, Pancreatic cancer types separately.

Table 14.5.3.1
 Summary of Positive Anti-Mogamulizumab Antibody Response at Post-Baseline and Infusion Reaction
 Safety Analysis Set

[figure not shown]
All Cancer Types

	All Subjects Exposed to Mogamulizumab
	N = xx
	n (%)
Number of Infusion Reactions (events)	xx
Number of Subjects who experienced Infusion Reactions	xx (xx.x)

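### SAP 4.12.3 labels subjects ADA-negative on a last sample that 4.12.1 will not call negative, and the incidence table neither counts unclassifiable subjects nor uses one baseline definition

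*SAP*

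**What the plan says.** SAP 4.12.1 gives each sample one of four statuses. A sample is positive if the confirmatory assay is positive. A screening-negative sample counts as negative only if the mogamulizumab concentration is known and no higher than the drug tolerance limit of 16000 ng/mL. (A screening-positive sample that fails confirmation is also negative.) Above that limit the sample is ADA-inconclusive. The fourth status, ADA-unknown, is defined thus: "The sample is negative in the screening assay and the serum KW-0761 concentration at the same timepoint is unknown".

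SAP 4.12.3 has only three on-treatment subject statuses: positive, negative and inconclusive. The negative status applies when the subject is not ADA-positive "at any time point and the sample ADA status at the last time point is not" ADA-inconclusive. Unknown is not mentioned.

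SAP 4.12.5 says that the ADA Analysis Set "will include all subjects that have both a baseline subject ADA status and at least one on-treatment subject ADA status". Overall incidence is the number of ADA-positive subjects "as a percentage of the total number of subjects in the ADA Analysis Set", and neutralizing incidence has the same denominator. Treatment-induced incidence is taken "as a percentage of the number of subjects whose sample ADA status before administration of mogamulizumab is" ADA-negative. Its numerator is defined in 4.12.3 by a negative baseline assay result, a different expression.

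In the shell for Table 14.1.1.3, the exclusion reasons for the ADA set are a missing baseline sample and "Did not have any post baseline sample". The shell for Table 14.5.2.1 has no entry for inconclusive or unknown subjects.

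**The concern.** The drug-tolerance rule in 4.12.1 exists because circulating drug can hide antibody, so a negative screen is not trusted unless the concentration is known to be low enough. The subject-level rule respects this for inconclusive samples but not for unknown ones. A subject can therefore be called ADA-negative on a sample that the same plan declines to call negative.

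Two further matters concern the percentages. First, subjects who cannot be classified stay in the overall and neutralizing denominators, and the summary table does not say how many there are, so a reader cannot tell how firm the incidence is. Second, the treatment-induced rate can count a subject in its numerator who is absent from its denominator.

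At stake is the interpretation of an exploratory objective (Protocol 5.3, SAP 2.3). The subject labels also appear in Listing 16.2.14.1.2. They could carry into the analyses of immunogenicity against safety, efficacy and PK that Protocol 12.6 says may be explored and that SAP section 4 assigns to separate plans. There, unknown subjects would sit in the negative comparison group.

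**Working it through.** **Step 1. Apply the rules to a never-positive subject.** The inputs are the definitions in SAP 4.12.1, 4.12.3 and 4.12.5.

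| Last sample | Negative under 4.12.1? | Subject label under 4.12.3 | In overall numerator? | In overall denominator? |
|---|---|---|---|---|
| ADA-negative | yes | ADA-negative | no | yes |
| ADA-inconclusive | no | ADA-inconclusive | no | yes |
| ADA-unknown | no | ADA-negative | no | yes |

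The third row is the contradiction. The last two columns show that the label has no numerical effect: moving unknown subjects from negative to inconclusive leaves every 4.12.5 percentage as it was.

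**Step 2. What the full-set denominator does.** Let N be the ADA Analysis Set, x the ADA-positive subjects, and m the never-positive subjects whose last sample is inconclusive or unknown.

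- Planned overall incidence: x/N.
- Incidence among classifiable subjects: x/(N−m).
- Upper bound, if all m were truly positive: (x+m)/N.

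Taking the other classifications as correct, x/N is the lower end of the range x/N to (x+m)/N.

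**Step 3. Numbers.** The documents give no expected incidence and no expected unclassifiable share, so there is no planned figure to reproduce. N=188 is the maximum study size (SAP 4.2) and hence the largest possible ADA set. The values of x and m are assumptions.

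| x | m | x/N | x/(N−m) | (x+m)/N |
|---|---|---|---|---|
| 9 | 0 | 9/188 = 4.8% | 9/188 = 4.8% | 9/188 = 4.8% |
| 9 | 9 | 4.8% | 9/179 = 5.0% | 18/188 = 9.6% |
| 9 | 19 | 4.8% | 9/169 = 5.3% | 28/188 = 14.9% |
| 9 | 38 | 4.8% | 9/150 = 6.0% | 47/188 = 25.0% |
| 19 | 38 | 19/188 = 10.1% | 19/150 = 12.7% | 57/188 = 30.3% |

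The planned figure does not move with m, so it conveys nothing about m.

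**Step 4. The treatment-induced rate.** Let d be the subjects with baseline sample status ADA-negative, t those among them who turn positive, and k the subjects with baseline status ADA-unknown who turn positive.

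A baseline-unknown sample is screening-negative. Read literally, its assay result is negative and the subject qualifies for the numerator. Its sample status is not ADA-negative, so the subject is outside the denominator (N1 in Table 14.5.2.1). The reported rate is then (t+k)/d, which exceeds t/d whenever k>0. With assumed values d=100, t=5 and k=1, it is 6/100 = 6.0% against 5/100 = 5.0%.

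This denominator depends on baseline status only, so it also keeps subjects who cannot be classified on treatment, which acts in the other direction.

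**The case against.** The strongest reply is that the full-set denominator is explicit, pre-specified and reproducible, and that the alternative is no better as an estimate. That is right about the alternative. The rate x/(N−m) drops only never-positive subjects, while an ever-positive subject stays in whatever the last sample shows. If most of those dropped are truly negative, it overstates incidence. It serves as a sensitivity figure, not as the correct value.

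Unknown samples should also be uncommon. Protocol Table 10.2-1 schedules a PK sample at every ADA time point, so an unknown status requires a missing or unusable PK result. At baseline the case is more remote still: prior mogamulizumab is excluded (Protocol 7.3), so masking by drug is not expected, and the phrase about the assay result could be read as meaning sample status, which would remove the mismatch. This limits the likely size of the problem. It does not settle which reading the programmer should use.

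Finally, the information is traceable. Listing 16.2.14.1.1 prints each sample's status, including inconclusive and unknown, and inconclusive is its own subject category. That stands, but a reader of Table 14.5.2.1 would have to rebuild the count by hand, and the subject listing would show unknown subjects as negative.

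A reader might infer that calling unknown subjects negative lowers the reported incidence. It does not, because the ADA-negative subject label is in no formula. Nor does every inconsistency act downwards: the baseline mismatch would raise the treatment-induced rate. The point should not be extended to the by-visit Table 14.5.1.1 either. Its denominator is "Number of subjects with valid measurements for anti-mogamulizumab antibody at the specified visit", and valid is not defined.

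**Conclusion.** The point holds in three limited parts.

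1. The subject-level negative rule in 4.12.3 contradicts the sample-level rule in 4.12.1 for a last sample of ADA-unknown. This follows from the text alone, and nothing elsewhere in either document corrects it. It mislabels subjects but changes no percentage.
2. Overall incidence is reported only as the lower end of its possible range, without the count needed to judge the width. Neutralizing incidence shares the same denominator. The width is m/N, which is zero if no never-positive subject ends on an inconclusive or unknown sample. The documents give no basis for estimating m. Its unknown component is probably small; inconclusive subjects may matter more.
3. Read literally, the treatment-induced rate can have a numerator that is not contained in its denominator, which would raise it.

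The documents do not support saying that incidence is understated by a known amount: that would need both the number of unclassifiable subjects and their true status. No 4.12.5 percentage enters the dose-finding rule, the Simon futility rule or the response-rate analysis. The changes are still worth making, because the rules as written conflict and the correction is cheap.

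**What to change.** - **4.12.3:** require for a negative call that the last sample is neither ADA-inconclusive nor ADA-unknown. Class never-positive subjects who end on ADA-unknown with the inconclusive subjects, or give them a category of their own.
- **4.12.5 and Table 14.5.2.1:** report the number of unclassifiable subjects. Keep the planned full-set incidence and put incidence among classifiable subjects beside it, labelled as a sensitivity figure.
- **Treatment-induced rate:** use baseline sample status ADA-negative in both numerator and denominator, and point the cross-reference for that status to 4.12.1, where it is defined, instead of 4.12.3.

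The cost is a few words in two SAP sections, plus one count and one companion rate in one table. No new data are needed, because sample-level status is already planned for Listing 16.2.14.1.1, and the planned overall incidence figure is unchanged.

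### An unknown last sample makes a never-positive subject ADA-negative, and unreadable subjects stay in the denominator, so overall and neutralizing ADA incidence are lower bounds

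*SAP*

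**What the plan says.** SAP 4.12.1 gives each sample one of four states. A screening-negative sample is ADA-negative only if the mogamulizumab concentration at that time is at or below the assay's tolerance limit. If the concentration is "above the drug tolerance limit (16000 ng/mL"), the sample is ADA-inconclusive. The fourth state is for a missing drug level: "ADA-unknown: The sample is negative in the screening assay and the serum KW-0761 concentration at the same timepoint is unknown" (KW-0761 is mogamulizumab).

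SAP 4.12.3 has only three on-treatment subject states: positive, negative and inconclusive. A baseline-negative subject is positive if "one or more assay results of the samples after administration of mogamulizumab are positive". The negative rule has two parts: the subject was never ADA-positive "and the sample ADA status at the last time point is not" ADA-inconclusive. There is no subject-level unknown.

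SAP 4.12.5 admits to the ADA Analysis Set all subjects who "have both a baseline subject ADA status and at least one on-treatment subject ADA status". ADA-inconclusive is such a status, so those subjects are included. Overall incidence is the number of ADA-positive subjects "as a percentage of the total number of subjects in the ADA Analysis Set", and neutralizing incidence has the same denominator. Treatment-induced incidence is given "as a percentage of the number of subjects whose sample ADA status before administration of mogamulizumab is" ADA-negative.

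Table 14.5.2.1 has columns for pre-existing, anytime, treatment-induced, treatment-boosted and neutralizing incidence. It has none for inconclusive or unknown subjects.

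**The concern.** SAP 4.12.1 accepts that a negative screen does not rule out ADA when drug is high or its level is missing. SAP 4.12.3 keeps that caution for one of the two cases and drops it for the other. A never-positive subject with no readable sample at all can be labelled ADA-negative.

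The denominator raises a separate question. A subject in whom the assay could not exclude ADA adds to the denominator and cannot add to the numerator, and so has the same effect on the percentage as a true negative. Immunogenicity is the second exploratory objective. A reader of the summary table could not tell a low incidence from a high share of unreadable subjects.

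**Working it through.** The SAP states no expected ADA incidence or unreadable share, so there is no planned figure to reproduce.

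**Step 1: what the subject rule does.** Write P, N, I and U for a positive, negative, inconclusive or unknown sample, and take a baseline-negative subject. Applying 4.12.3:

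- PNNN and PIII are positive, whatever the last sample shows.
- NNNI is inconclusive, although three samples were readable and negative.
- IIIN is negative on one readable sample.
- IIIU and UUUU are negative with no readable sample.

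For three samples there are 3 × 3 × 3 = 27 never-positive sequences. Those not ending in I number 3 × 3 × 2 = 18, and all are called negative. Of these, 17 contain at least one I or U (all but NNN). Four contain no N: IIU, IUU, UIU and UUU. These are counts of possible patterns, not of expected subjects.

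**Step 2: which rule moves incidence.** Let N be the ADA Analysis Set, k the ADA-positive subjects and U the unreadable never-positive subjects. Overall incidence in 4.12.5 is k/N. Moving a subject between negative, inconclusive and unknown changes neither k nor N. The unknown default therefore mislabels subjects but leaves k/N as it is. The denominator rule is what makes k/N a lower bound: the value could lie anywhere from k/N to (k + U)/N. Among evaluable subjects (positive plus negative) it is k/(N − U), which is k/N multiplied by N/(N − U).

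**Step 3: size for assumed values.** N = 188 is the enrolment ceiling in SAP 4.2; k = 19 and the values of U are assumptions.

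| Unreadable U | SAP figure 19/188 | Evaluable 19/(188 − U) | Upper bound (19 + U)/188 |
|---|---|---|---|
| 9 (5%) | 10.1% | 10.6% | 14.9% |
| 19 (10%) | 10.1% | 11.2% | 20.2% |
| 38 (20%) | 10.1% | 12.7% | 30.3% |
| 56 (30%) | 10.1% | 14.4% | 39.9% |
| 94 (50%) | 10.1% | 20.2% | 60.1% |

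With U = 0 nothing changes.

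**Step 4: could samples be unreadable?** The clinical pharmacology sections are redacted, so this rests on assumptions: a one-compartment model, 70 kg, 1 mg/kg, volume V of 3, 4.5 or 6 L, and half-life of 8, 12, 17 or 22 days (12 scenarios). Doses fall on Days 0, 7, 14 and 21, then every 14 days. Concentration at time t is the sum over earlier doses of (70 mg/V) × exp(−ln 2 × time since dose/half-life).

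| Sample | Scenarios above 16000 ng/mL | Range |
|---|---|---|
| Cycle 2 Day 1, pre-dose | 11 of 12 | 12,752 to 55,424 ng/mL |
| Cycle 4 Day 1, pre-dose | 7 of 12 | 4,997 to 44,372 ng/mL |
| 100 days after last dose | 0 of 12 | maximum about 3,200 ng/mL |

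The last row holds whether treatment stops after Cycle 1, 2 or 4 or at 96 weeks.

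**Step 5: which sample is last?** Protocol Table 10.2-1 schedules ADA samples before dosing in Cycles 1 to 4, 8 and 12, and at Day 100-110 after the last dose. SAP 4.12.3 assigns subject status for the period of mogamulizumab dosing, which suggests that Day 100-110 is excluded. Table 14.5.1.1 lists that visit, and its overall row counts any post-baseline positive, which suggests that it is included. Protocol 9.5 stops ADA sampling for subjects ongoing at data cutoff, so some subjects may never give that sample.

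**Step 6: treatment-induced incidence.** Its numerator needs a negative baseline assay result; its denominator needs a baseline sample status of ADA-negative. A subject whose baseline status is unknown can enter the numerator only. Assumed example: 170 baseline-negative, 18 baseline-unknown and 19 induced give 19/170 = 11.2%, against 19/188 = 10.1%. This mismatch pushes the figure up.

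**The case against.** A reader might infer that a subject is called ADA-negative on the last sample alone. The text does not say that: one positive sample makes a baseline-negative subject positive, and the last sample only divides never-positive subjects into negative and inconclusive.

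A reader might also infer that ADA incidence as a whole is biased low. That is too broad. Step 2 shows that the labelling rules leave overall incidence unchanged, Step 6 shows that treatment-induced incidence can move up, and pre-existing incidence uses baseline samples only.

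Nor is the information wholly hidden. Listing 16.2.14.1.1 prints each sample's ADA status beside the drug concentration, with inconclusive and unknown among its example entries, and Listing 16.2.14.1.2 gives subject status. What is missing is a summary count. The per-visit denominators in Table 14.5.1.1 rest on valid measurements, a term not defined for inconclusive or unknown samples.

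Finally, a complete and stated denominator is a defensible choice for a descriptive percentage, and the unreadable share may be close to nil if the washed-out follow-up sample is used. All of this stands. It narrows the point and lowers its weight. It does not remove the contradiction between 4.12.1 and 4.12.3, or the need to show how many subjects were unreadable.

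**Conclusion.** The point holds in this limited form. Among never-positive subjects, the last sample alone separates negative from inconclusive, and a last sample of unknown status becomes negative against the SAP's own sample definitions. Overall and neutralizing incidence are lower bounds whenever some never-positive subjects are unreadable.

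The size cannot be taken from the documents. Under the assumed pharmacokinetics, inconclusive last samples all but vanish for subjects whose Day 100-110 sample counts and has a drug level. They could be common if only on-treatment pre-dose samples count. The Step 4 scenarios concern samples, not subjects, and the unreadable shares in Step 3 are illustrations, so neither supports a claim of substantial bias. The point is minor: the endpoint is exploratory and descriptive, and no test or decision depends on it.

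**What to change.** In SAP 4.12.3:

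- do not let an ADA-unknown last sample default to negative; class such never-positive subjects as inconclusive/unknown;
- state how earlier inconclusive or unknown samples count, so that IIIN and NNNU, for example, each have a defined result;
- state whether the Day 100-110 sample can be the last time point.

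In SAP 4.12.5 and Table 14.5.2.1, add the number of inconclusive/unknown subjects, and report overall and neutralizing incidence on both the full ADA Analysis Set and the evaluable subjects (positive plus negative).

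The cost is SAP wording and added table entries; no new samples are needed. The evaluable denominator has its own drawback: it is smaller, and it can overstate incidence, because positive subjects are always kept while never-positive subjects are dropped when unreadable. The two figures should therefore stand side by side, and neither should replace the other.
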